HCV reinfection is defined as confirmed HCV RNA  $\geq$  LLOQ after the end of treatment in a subject who had HCV RNA  $<$  LLOQ at Final Treatment Visit, along with the post-treatment detection of a different HCV genotype, subtype, or clade compared with baseline, as determined by phylogenetic analysis of the NS3 or NS5A, and/or NS5B gene sequences. Reinfection in the case of the same HCV subtype is defined as a clade switch, as indicated by the lack of clustering between the baseline and post-treatment sequences by phylogenetic analysis. If phylogenetic analysis is not possible due to technical difficulties, HCV reinfection may be determined with a confirmed HCV genotype or subtype switch by the Versant HCV Genotype Inno-LiPA Assay v2.0 or Sanger assay.

Post-treatment relapse is defined as described earlier (**Relapse12**, **Relapse24**, **Relapseoverall**), and no genotype, subtype, or clade switch compared with baseline as determined by phylogenetic analysis of the NS3 or NS5A gene sequences. If phylogenetic analysis is not possible due to technical difficulties, the subject will be defined as having a post-treatment relapse unless an HCV genotype or subtype switch is confirmed by the Versant HCV Genotype Inno-LiPA Assay v2.0 or Sanger assay.

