### **Reasons for SVR12 Non-Response**

Subjects who do not achieve SVR12 (SVR12 non-responders) will be categorized as having:

1. On-treatment virologic failure (see **On-treatment virologic failure** definition, if a subject meets both definitions of **Breakthrough** and **EOT failure**, he or she will be categorized as **Breakthrough** only);
2. HCV reinfection (see definition described earlier);
3. Relapse12 (see **Relapse12** definition);
4. Prematurely discontinued study drug with no on-treatment virologic failure (defined as any SVR12 non-responder who prematurely discontinued study drug [study drug duration < 52 days for subjects assigned to 8 weeks of treatment, and < 77 days for subjects extended to 12 weeks of treatment] and did not meet the **On-treatment virologic failure** definition);
5. Missing follow-up data in the SVR12 window (defined as any subject who completed study drug without data in the SVR12 window after applying the imputation rules and not meeting the definitions of [1], [2], [3], or [4]);
6. Other (defined as any SVR12 non-responder not meeting the definitions of [1] – [5]).

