## 10.8 Resistance Analyses

For all subjects, full length NS3/4A or NS5A from baseline samples will be sequenced by next generation sequencing (NGS). For subjects who experience virologic failure (on-treatment virologic failure or post-treatment relapse as defined in Section 10.1), full length NS3/4A and NS5A genes from the first sample after virologic failure with HCV RNA  $\geq$  1000 IU/mL will be sequenced by NGS. An appropriate subtype specific prototypic reference sequence will be used for comparison with sequences from samples. Subjects who experience virologic failure (VF) will be referred to as subjects in the primary virologic failure (PVF) population, and a listing by subject that includes HCV genotype/subtype, IL28B genotype, reason for SVR12 non-response, time point(s) sequenced as closest to time of VF, and HCV RNA value at the VF time point(s) will be produced for these subjects. In addition, all listings described below will display HCV genotype/subtype and reason for SVR12 non-response in the subject identifier for each subject. A separate listing will summarize all subjects in the PVF population for whom no sequencing was performed (e.g., lost to follow-up while HCV RNA  $\leq$  1000 IU/mL).

Subjects treated with study drug who do not achieve SVR12 due to reasons other than virologic failure (prematurely discontinued study drug with no on-treatment virologic failure, HCV reinfection, missing SVR12 data, or other reasons as described in Section 10.1, Reasons for SVR12 Non-Response), but have a time point with HCV RNA  $\geq$  1000 IU/mL after treatment discontinuation will have the sample at that time point sequenced. These subjects will be referred to as the non-PVF population. A listing of all subjects in the non-PVF population with post-baseline sequencing available will be created that is similar to the listing of subjects in the PVF population with post-baseline sequencing available.

Included time points for analyses on samples from subjects who do not achieve SVR12 are 1) the sample closest in time after failure/discontinuation with an HCV RNA level of  $\geq$  1000 IU/mL, and 2) 24 weeks post-DAA treatment, provided that resistance-associated substitutions were detected by NGS at the time of HCV virologic failure/treatment discontinuation.

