**Table 6. Signature Amino Acid Positions and the Key Subset of Amino Acid Positions**

Target	Signature Amino Acid Positions	Key Subset of Amino Acid Positions
GT1 NS3	36, 43 (GT1a only), 54, 55, 56, 80, 107, 122, 132 (GT1a only), 155, 156, 158, 168, 170, 175 (GT1b only)	155, 156, 168 (all GTs)
GT2, 3, 4, 5, 6 NS3	36, 43, 54, 55, 56, 80, 155, 156, 166 (GT3 only), 168	
GT1 NS5A	24, 28, 29, 30, 31, 32, 54 (GT1b only), 58, 62, 92, 93	24, 28, 30, 31, 58, 92, 93 (all GTs)
GT2, 3, 4, 5, 6 NS5A	24, 28, 29, 30, 31, 32, 58, 92, 93	

The following definitions will be used in the resistance analyses:

- Baseline polymorphism: a polymorphism by NGS in a baseline sample ( $\geq 2\%$  or  $\geq 15\%$  prevalence within a subject's viral population depending on polymorphism frequency threshold utilized) that was not present in the appropriate prototypic reference amino acid sequence for a given DAA target (NS3/4A or NS5A).
- Polymorphism/substitution at a signature amino acid position: polymorphism (relative to reference) present in a baseline sample or substitution (relative to baseline) present in post-baseline sample at a signature amino acid position.
- Post-baseline substitution: an amino acid substitution in a post-baseline time point sample that was not detected at baseline ( $< 2\%$ ) in the subject and is detectable in  $\geq 2\%$  of the sequences from the post-baseline sample.
- Enriched substitution: substitution present in both the baseline and a post-baseline sample whose prevalence in the post-baseline sample is at least 20 percentage points greater than the prevalence in the baseline sample [(post-baseline % – baseline %)  $\geq 20$ ].
- Treatment-emergent substitution: A post-baseline substitution or an enriched substitution.

**Analysis 1:** The following analyses will be provided for all subjects, separated by HCV subtype:

- A listing of all baseline polymorphisms (2% detection threshold) at signature amino acid positions for each DAA target (NS3/4A and NS5A) (ITT).
- A listing of all baseline polymorphisms (15% detection threshold) at non-signature amino acid positions for each DAA target (NS3/4A and NS5A) for subjects in the PVF population.
- A by subject listing of baseline polymorphisms (15% detection threshold) at signature amino acid positions in subjects with polymorphisms across both NS3 and NS5A, or those with multiple baseline polymorphisms within any one target (NS3/4A or NS5A).

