**Analysis 4:** The following analyses will be performed for subjects who do not achieve SVR12 and who have post-baseline resistance data available:

- Listings by subject of all treatment-emergent substitutions relative to the baseline amino acid sequences will be provided for each DAA target (NS3/4A and NS5A).
- Listings by subject and time point of all post-baseline substitutions at signature amino acid position relative to the baseline amino acid sequence will be provided for each DAA target (NS3 and NS5A).
- The persistence of post-baseline variants at signature resistance-associated amino acid positions for each target (NS3 and NS5A) from subjects will be assessed at Post-Treatment Week 24. Listings by subject and time point of all treatment-emergent variants will be provided for each DAA target (NS3 and NS5A).

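### SAP 10.8 Analysis 4 does not exclude reinfected subjects, so residues of a newly acquired strain would be listed as treatment-emergent substitutions

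*SAP*

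**What the plan says.** Analysis 4 in SAP 10.8 takes all subjects without SVR12 "who have post-baseline resistance data available". It yields three kinds of by-subject output: "Listings by subject of all treatment-emergent substitutions relative to the baseline amino acid sequences", post-baseline substitutions at signature positions, and the Week 24 persistence of signature-position variants. The comparator is the subject's own baseline sequence.

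Earlier in SAP 10.8, non-responders without virologic failure are described, with examples that include "prematurely discontinued study drug with no on-treatment virologic failure, HCV reinfection". If such a subject has HCV RNA of at least 1000 IU/mL after stopping treatment, the subject "will have the sample at that time point sequenced. These subjects will be referred to as the non-PVF population".

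SAP 10.1 defines reinfection as confirmed quantifiable HCV RNA after treatment, in a subject below LLOQ at the Final Treatment Visit, "along with the post-treatment detection of a different HCV genotype, subtype, or clade compared with baseline".

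The definitions beneath SAP Table 6 make a post-baseline substitution "an amino acid substitution in a post-baseline time point sample that was not detected at baseline" (below 2%) and present in at least 2% of post-baseline sequences. Every post-baseline substitution is a treatment-emergent substitution. Protocol 8.1.4 has the same Analysis 4 population and, in substance, the same definitions.

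**The concern.** A reinfected subject carries a virus that did not descend from the one treated. Where the new strain differs from the old, the difference was not selected by 8 weeks of GLE/PIB. The definitions test only whether a residue is new relative to baseline. They do not require the two samples to come from the same viral lineage.

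Evaluating the emergence and persistence of resistance-associated substitutions is a stated purpose of the post-treatment follow-up (Protocol 5.1). Protocol 3.2 accepts that the shorter duration may raise virologic failure and notes that NS5A substitutions can persist for years. At stake is whether the listings that serve this purpose show only changes in the treated virus.

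**Working it through.** The plan gives no count or power figure for this analysis, so the main check is a trace of the rules.

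**Does a reinfected subject enter Analysis 4, and with what label?**

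1. Reinfection is category 2 of the six reasons for SVR12 non-response (SAP 10.1), so the subject is a non-responder.
2. SAP 10.8 names reinfection in the sequenced non-PVF group, given a sample of at least 1000 IU/mL.
3. Analysis 4 is not limited to the PVF (virologic failure) population, whereas the non-signature listing in Analysis 1 is. The subject is in.
4. The virus differs from baseline by definition. Each residue below 2% at baseline and at 2% or more afterwards is a post-baseline substitution, hence treatment-emergent.
5. Week 24 sequence is used only if resistance-associated substitutions were detected at virologic failure or treatment discontinuation. A reinfected subject had no virologic failure and was below LLOQ at the Final Treatment Visit, so it is unclear whether this condition can be met. Entry to the persistence listing is possible but not automatic.

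**How does the plan treat reinfection elsewhere?**

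| Place | Handling |
|---|---|
| SAP 5.1.2, PP population | excluded |
| SAP 10.1, relapse | excluded |
| SAP 10.4.2, relapse analysis | summarized separately |
| SAP 10.8, Analyses 2 and 3 | excluded through mITT-GT-VF (SAP 5.1.4) |
| SAP 10.8, Analysis 4 | no exclusion |

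Analysis 4 is the exception, which points to an omission and not a choice.

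**How many subjects?** The documents give no reinfection rate. Two figures help:

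- Total non-virologic failure in the registrational program was 29/2369 = 1.2% (SAP 4.3.1). Reinfection is one component, beside early discontinuation and missing data. Applied to 330 subjects, the whole category is 0.012 × 330 ≈ 4.
- Among 117 + 65 = 182 treatment-naïve cirrhotic subjects treated for 12 weeks, the three failures were one early discontinuation and two with missing data (SAP 4.3.1). None was attributed to reinfection.

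An assumed reinfection rate of 0 to 1% gives 0 to 3.3 subjects. The top of that range would use most of the 1.2%, so zero or one is more in keeping with the documents.

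For comparison, expected virologic failures are 0.02 × 330 = 6.6 under the 98% PP assumption (Protocol 8.2), or 0.02 × 270 + 0.08 × 60 = 5.4 + 4.8 = 10.2 under the modelled 98% and 92% (Protocol 5.6.4.2).

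**The case against.** The strongest reply is that nothing in Analysis 4 is pooled or tested. Every output is a listing by subject, with no percentage or comparison. SAP 10.8 puts genotype/subtype and the reason for non-response in each subject identifier, and it provides a separate listing of non-PVF subjects with post-baseline sequence. The term treatment-emergent is defined purely against baseline, much as treatment-emergent adverse events are defined purely by timing (SAP 11.2.1). On this view only a label is at issue.

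Most of this stands, and it limits the consequence. A reader might infer that false resistance would be attributed to the shortened regimen. The plan contains no step that does so, and a careful reader can set the marked rows aside. The safeguard is still partial. The rows keep a label that does not describe them, and the only genotype determination set out in SAP 10.8 uses baseline samples, so the identifier is not stated to show the new strain.

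A reader might also infer that a strain switch will usually add entries at NS5A key positions, because polymorphisms there occur in 12.9% to 79.8% of subjects depending on genotype (Protocol 3.0). Those are prevalences against a reference, not differences between two strains. For a same-subtype clade switch, assuming two independent strains and the genotype-level prevalence p, a difference needs at least one of them to carry a polymorphism. Its chance is therefore at most 1 − (1 − p)²:

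- GT1: 1 − 0.732² = 46%
- GT3: 1 − 0.779² = 39%
- GT5: 1 − 0.871² = 24%

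The ceiling is higher for GT2, GT4 and GT6. The 2% threshold, the wider set of signature positions or a genotype switch would also raise it. The cited prevalences nevertheless do not establish that such entries are usual.

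**Conclusion.** The point holds on the text. As written, Analysis 4 would list a new strain's residues as treatment-emergent, and the plan separates reinfection in the related analyses shown above. It is worth correcting, but it is minor.

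- Only by-subject descriptive listings are affected. The primary and key secondary SVR12 tests and resistance Analyses 2 and 3 are untouched.
- It arises only for a reinfected SVR12 non-responder with a sample of at least 1000 IU/mL. The number is probably small and may be zero, in which case no harm follows.
- The persistence listing is affected only if the condition for Week 24 sequencing is met.

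A reader might infer that a quarter to a third of listed subjects could be affected: 3.3/(3.3 + 10.2) = 24% to 3.3/(3.3 + 6.6) = 33%. The documents do not support that as a working figure. It takes the extreme of an assumed range, supposes that every reinfected subject has a sequenceable sample, and leaves other sequenced non-PVF subjects out of the denominator.

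The trace itself rests on no numerical assumption. The statement about size rests on the registrational non-virologic failure rate being a fair guide to this trial.

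**What to change.** In SAP 10.8, restrict the treatment-emergent and persistence listings of Analysis 4 to SVR12 non-responders not classified as HCV reinfection. Add a separate listing of reinfected subjects showing signature-position polymorphisms against the reference for the new subtype, labelled as not treatment-emergent. Using the new subtype also settles which signature positions apply after a genotype switch, since SAP Table 6 differs between GT1 and the other genotypes.

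The cost is a short SAP edit, one filter and one extra listing. No data are lost, and no new samples or assays are needed. Protocol 8.1.4 has the same gap and can be aligned at the next amendment. A separate amendment for this alone is not warranted, because amendments go through ethics review (Protocol 9.1).

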### **HCV Genotype/Subtype**

Phylogenetic analysis will be conducted on HCV NS3/4A and/or NS5A sequence from baseline samples from all subjects in order to accurately determine genotype/subtype. If the phylogenetic analysis is not available, then the result from Sanger sequencing of a region of NS5B by AbbVie or by the Central laboratory will be used to determine the subject's HCV genotype/subtype, if available. Finally, if neither the phylogenetic analysis result nor the Sanger sequencing assay results is available, then the Inno-LIPA assay results from the Central laboratory will be used to categorize the subject. This

information will be presented in summaries of efficacy subgroup analyses and resistance analyses.

A summary of HCV subtype as provided by the central laboratory (Sanger sequencing or Inno-LiPA 2.0 Assay [if Sanger sequencing not available]) versus phylogenetic analysis also will be provided.

## **10.9 Patient Reported Outcomes**

The following instruments will be used to collect patient reported outcomes (PROs): TSQM, SF-36v2 and FSS. Missing data for each measurement will be handled as described in Section 6.3.

The TSQM is a 14-item instrument and includes assessments of satisfaction with a medication's effectiveness (Effectiveness, three items), lack of side effects (Side Effects; five items), convenience (three items) and the subject's global satisfaction (Global Satisfaction; three items). No imputation will be applied to each measurement for missing items. TSQM scores range from 0 – 100 with higher scores indicating better satisfaction.

The SF-36v2 measures dimensions of a patient's functional health and well-being in 8 domains and also provides 2 summary scores that characterize a patient's mental (Mental Component Summary; SF-36-MCS) and physical (Physical Component Summary; SF-36-PCS) health status. Imputation will be applied to each domain as described in Section 6.3. The score for each of the 8 domains ranges from 0 to 100 and will be normalized according to the user manual. The standardization of the normalized scores will provide the norm-based scores with a mean of 50 and a SD of 10. The two summary scores are based on the norm-based scores. Per the SF-36v2 instrument manual, score for any item with multiple responses will be set to "missing." Subject's responses to the SF-36v2 will be summarized for the SF-36-PCS and SF-36-MCS measures and eight individual domain measures.

The FSS measures the impact of fatigue over the past week on specific types of functioning. The survey consists of 9 questions using a 7-point Likert scale. A total score

is calculated as the average of the individual item responses (adding up all the answers and dividing by nine). Higher FSS scores indicate a higher degree of impact of fatigue. Imputation will be applied to the total score as described in Section 6.3.

Summary statistics (n and mean) at each visit and for the change from baseline (n, mean, SD, minimum and maximum) to each applicable post-baseline timepoint will be provided for SF-36v2 (SF-36-PCS and SF-36-MCS and eight individual domains) scores and for the FSS total score. In addition, summary statistics (n, mean, SD, median, minimum and maximum) for the TSQM subscales (global satisfaction, convenience, effectiveness, side effects) at Weeks 2, 4, and 8 will be provided.

The following analyses of PROs also will be performed:

- Number and percentage of subjects who have experienced an increase from baseline at each applicable timepoint of greater than or equal to 3 points in the SF-36-MCS and SF-36-PCS;
- Number and percentage of subjects who have experienced an increase from baseline at each applicable timepoint of greater than or equal to 5 points in the SF-36-MCS and SF-36-PCS;
- Number and percentage of subjects who have experienced an increase from baseline at each applicable timepoint of greater than or equal to 5 points in the SF-36 domain scores;
- Number and percentage of subjects who have experienced an increase from baseline at each applicable timepoint of greater than or equal to 0.7 in the FSS total score;
- Number and percentage of subjects who have experienced an increase from baseline at each applicable timepoint of greater than or equal to 1 in the FSS total score.

If a subject starts another treatment for HCV, then all PRO values for this subject measured on or after the start date of the new HCV treatment will be excluded from analyses.

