The SF-36v2 is a general Health Related Quality of Life (HRQoL) instrument with extensive use broad variety of health conditions and is the standard in literature for HCV. The SF-36v2 instrument comprises 36 total items (questions) targeting a subject's functional health and well-being in 8 domains (physical functioning, role physical, bodily pain, general health, vitality, social functioning, role emotional and mental health). Domain scores are also aggregated into a Physical Component Summary score and a Mental Component Summary score. Higher SF-36v2 scores indicate a better state of health. The SF-36v2 should require approximately 10 minutes to complete.

Fatigue Severity Scale (FSS)

The FSS measures the impact of fatigue over the past week on specific types of functioning (e.g., motivation, exercise, physical functioning, carrying out duties, interfering with work, family, or social life). The survey consists of 9 questions using a 7-point Likert scale. A total score is calculated as the average of the individual item responses. The scale's psychometric properties have been confirmed in chronic hepatitis C and other diseases. The FSS should require approximately 5 minutes to complete.

PRO instruments should be consistently presented prior to any discussion of adverse events or any review of laboratory findings, including HCV RNA levels at each visit

where PROs are required throughout the study and in the following order: the TSQM (when applicable), the SF-36v2 and FSS. The Day 1 SF-36v2 and FSS questionnaires should be completed prior to drug administration on Day 1.

Enrollment and Assignment of Subject Numbers

All Screening activities must be completed and reviewed prior to enrollment. Subjects who meet all the Inclusion Criteria and none of the Exclusion Criteria at Screening will proceed to enrollment via the IRT system on Study Day 1.

Subject numbers will be unique 6-digit numbers and will begin with 100001 with the first three digits representing the investigative site, and the last three digits representing the subjects at that site. Enrolled subjects will keep their subject number throughout the study. Subject will be enrolled on Study Day 1 as described in Section [5.5.3](#).

Study Drug Compliance for Kits

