8.1.3 Patient Reported Outcomes

The handling of missing data for patient reported outcomes (PROs) will be as follows. If a respondent answers at least 50% of the items in a multi-item scale of the SF-36v2, the missing items will be imputed with the average score of the answered items in the same scale. In cases where the respondent did not answer at least 50% of the items, the score for that domain will be considered missing. The missing item of the FSS questionnaire will be imputed with the average score of the answered items as long as more than 50% of the items on the FSS are answered.

The mean change from baseline to each applicable post-baseline timepoint in the FSS total score and the SF-36v2 Mental Component Summary (SF-36-MCS) and Physical Component Summary SF-36-PCS scores will be summarized descriptively at each visit. The TSQM subscales (global satisfaction, convenience, effectiveness, side effects) will be summarized descriptively at Weeks 2, 4, and 8.

The following analyses of patient reported outcomes (PROs) also will be performed:

- Number and percentage of subjects who have experienced an increase from baseline at each applicable timepoint of greater than or equal to 3 points in the SF-36-MCS and SF-36-PCS;
- Number and percentage of subjects who have experienced an increase from baseline at each applicable timepoint of greater than or equal to 5 points in the SF-36-MCS and SF-36-PCS;
- Number and percentage of subjects who have experienced an increase from baseline at each applicable timepoint of greater than or equal to 5 points in the SF-36 domain scores;
- Number and percentage of subjects who have experienced an increase from baseline at each applicable timepoint of greater than or equal to 0.7 in the FSS total score;
- Number and percentage of subjects who have experienced an increase from baseline at each applicable timepoint of greater than or equal to 1 in the FSS total score.

Additional analyses of PROs will be performed as useful and appropriate.

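### The FSS threshold tables count rises of 0.7 and 1 point, but a higher FSS score means worse fatigue, so they count worsening and leave out every improver

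*SAP*

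**What the plan says.** SAP section 10.9 defines the FSS total as the mean of nine items, each on a 7-point scale, and gives its direction: "Higher FSS scores indicate a higher degree of impact of fatigue". It then lists five counts of subjects who pass a threshold of change from baseline. Three concern the SF-36, the first being an "increase from baseline at each applicable timepoint of greater than or equal to 3 points in the SF-36-MCS and SF-36-PCS". The last two concern the FSS: an "increase from baseline at each applicable timepoint of greater than or equal to 0.7 in the FSS total score" and an "increase from baseline at each applicable timepoint of greater than or equal to 1 in the FSS total score". Protocol section 8.1.3 carries the same five bullets.

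For the SF-36, Protocol section 5.3.1.1 says "Higher SF-36v2 scores indicate a better state of health". The FSS description in that section does not say which end of the scale is worse; only the SAP does.

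The other FSS output is descriptive. Protocol section 8.1.3 plans a summary of "The mean change from baseline to each applicable post-baseline timepoint in the FSS total score", and SAP section 10.9 specifies n, mean, SD, minimum and maximum of the change.

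**The concern.** The five bullets share one stem and one direction, but the two instruments run opposite ways. A rise on the SF-36 is an improvement; a rise on the FSS is a deterioration. A programmer who follows the SAP to the letter will code the FSS criteria as change of +0.7 or more and +1 or more, and so produce tables of worsening. These will stand beside SF-36 tables of improvement with matching titles.

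Two things are at stake. A reader who takes the set as parallel, particularly one working from the Protocol, which does not state the FSS direction, may take a percentage who worsened for a percentage who benefited. And the proportion of subjects whose fatigue eased by a set amount is not planned anywhere.

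**Working it through.** The plan states no figure to reproduce for these tables. The check is one of sign, followed by an illustration of size.

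**Direction against counting rule**

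- SF-36 (Protocol 5.3.1.1): higher is better. Rule: change ≥ +3 or ≥ +5. This counts improvement.
- FSS (SAP 10.9): higher is worse. Rule: change ≥ +0.7 or ≥ +1. This counts worsening.

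**Two example subjects**

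- FSS 4.0 at baseline, 5.0 later: change = 5.0 - 4.0 = +1.0, more fatigue. Counted at both cut-offs.
- FSS 5.0 at baseline, 4.0 later: change = 4.0 - 5.0 = -1.0, less fatigue. Counted at neither.

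Any improver has a change below 0 and so cannot reach +0.7 or +1. This holds at every visit.

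**What the cut-offs mean in items.** The total is the sum of nine items divided by nine. With no missing items:

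- 0.7 × 9 = 6.3, so the item sum must rise by at least 7 points (7/9 = 0.78).
- 1 × 9 = 9, so it must rise by at least 9 points.

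Both are rises towards greater fatigue.

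**Illustration of size.** The documents give no mean or SD for FSS change, so the inputs here are assumptions. Take the change as normal with mean m (negative means less fatigue) and SD s. Then, for cut-off t:

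- as written, P(change ≥ t) = 1 - Φ((t - m)/s)
- reversed, P(change ≤ -t) = Φ((-t - m)/s)

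For example, with m = -0.4, s = 1.3 and t = 0.7:

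- as written: 1 - Φ((0.7 + 0.4)/1.3) = 1 - Φ(0.846) = 0.20
- reversed: Φ((-0.7 + 0.4)/1.3) = Φ(-0.231) = 0.41

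Over a range of assumptions:

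| Assumed mean | Assumed SD | ≥ 0.7 as written | ≥ 0.7 reversed | ≥ 1 as written | ≥ 1 reversed |
|---|---|---|---|---|---|
| 0 | 1.0 | 24.2% | 24.2% | 15.9% | 15.9% |
| 0 | 1.5 | 32.0% | 32.0% | 25.2% | 25.2% |
| -0.3 | 1.0 | 15.9% | 34.5% | 9.7% | 24.2% |
| -0.3 | 1.5 | 25.2% | 39.5% | 19.3% | 32.0% |
| -0.5 | 1.0 | 11.5% | 42.1% | 6.7% | 30.9% |
| -0.5 | 1.5 | 21.2% | 44.7% | 15.9% | 36.9% |
| -0.8 | 1.0 | 6.7% | 54.0% | 3.6% | 42.1% |
| -0.8 | 1.5 | 15.9% | 52.7% | 11.5% | 44.7% |

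The two rules agree only when the mean change is zero. At a given SD, the more fatigue eases on average, the smaller the planned percentage becomes and the larger the percentage of improvers that it leaves out.

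**The case against.** The strongest reply is that the intent is inferred. Neither document calls these counts responder analyses or says that they measure improvement. A count of worsening fatigue would not be absurd: Protocol section 3.0, Table 3, lists fatigue in 14.6% of subjects, and in 11.4% as drug-related. The scale direction is printed in the same SAP section as the bullets, and a table titled as an increase would be literally correct.

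That stands in part. A copying slip from the SF-36 bullets is likely but not proven, and misreading is a risk rather than a certainty. But nothing labels the counts as worsening. Read as deliberate, the plan would count only worsening on the FSS and only improvement on the SF-36, with no explanation.

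It also stands that other output limits the damage. The mean change would show the average direction, and the minimum would show the largest individual improvement. Protocol section 8.1.3 allows further PRO analyses, so a count of decreases could be added later, though it would not be pre-specified.

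Finally, the FSS is outside the fixed testing sequence and carries no hypothesis test. The SVR12 conclusions and the type I error are untouched.

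**Conclusion.** The point holds. By the SAP's own statement of scale direction, both FSS threshold tables count only subjects whose fatigue worsened. They exclude every improver at both cut-offs and every visit, and no count of decreases is planned in either document. This rests on no assumption. That the tables were meant to show improvement is an inference from the parallel SF-36 bullets.

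The numerical gap depends wholly on the assumed distribution of change. Over assumed mean changes of 0 to -0.8 and SDs of 1.0 to 1.5, the 1-point table would show 3.6% to 25.2% as written, against 15.9% to 44.7% if it counted improvers.

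The consequence is confined to descriptive patient-reported outcome tables, but the correction should be made.

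**What to change.** In SAP section 10.9 and Protocol section 8.1.3, change the two FSS bullets to count subjects with a decrease from baseline of at least 0.7 and of at least 1, and label the tables as improvement in fatigue. If worsening is also of interest, keep the increase versions as separate tables labelled as worsening. This serves either intent. Stating the FSS direction in Protocol section 5.3.1.1, as is already done there for the SF-36, would remove the remaining ambiguity.

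The cost is one word in each of two bullets per document, plus the labels. No new data and no new assessments are needed. The Protocol edit is a formal revision, and Protocol section 9.1 requires ethics approval of amendments before design changes are implemented. The SAP correction governs the programming, so it can be made first and the Protocol text aligned at the next amendment.
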